
Research with Prisoners? No

If yes, complete the Prisoners in Research Form and upload to IRBNet as supporting documentation

Research with Pregnant Women? No

Research with any other vulnerable population (e.g. cognitively impaired, economically disadvantaged, etc.)? please describe

The first phase of this study involves research with people at risk of HIV (i.e., key populations) and people living with HIV, many of whom are vulnerable populations in the context of Malaysia. For example, men who have sex with men and transgender women are at risk of HIV. In Malaysia, civil and religious laws criminalize same-sex sexual behavior and illicit drug use.

5. RESEARCH ABSTRACT

Please provide a brief description in LAY language (understandable to an 8th grade student) of the aims of this project.

Clinicians who stigmatize people at risk of or living with HIV provide worse HIV testing, treatment, and linkage to care services to these populations. To date, the vast majority of stigma-reduction interventions for clinicians have occurred in single healthcare facilities. We propose to deliver evidence-based stigma reduction tools through a popular teletraining platform for clinicians, Project ECHO[®]. Project ECHO[®] (Extension for Community Healthcare Outcomes) has trained, supported, and empowered 70,000+ clinicians to provide a wide range of specialty care services in 37+ countries globally, including HIV testing, prevention, and linkage to care. It uses a "hub and spoke" model wherein non-specialists in community setting "spokes" learn from and collaborate with specialists at academic "hubs" via

videoconferencing technology (i.e., Zoom software). By delivering stigma-reduction tools through Project ECHO®, we could substantially extend the reach of stigma-reduction interventions for clinicians.

There are four phases of our project:

- **Phase 1:** We will explore experiences of stigma among people at risk of and living with HIV using Photovoice, a qualitative data collection technique involving photography and story-telling (n=35).
- **Phase 2:** We will explore clinicians' perspectives on an intervention to address stigma through online focus groups (n=40).
- **Phase 3:** We will conduct a brief pre-test of our intervention protocol with a small sample of clinicians (n=5).
- **Phase 4:** We will pilot test our intervention protocol among clinicians, comparing it to two control conditions (n=78). Our intervention materials will include Photovoice presentations created by participants in Phase 1 of the study. Importantly, these presentations will be screened to ensure that they do not contain identifying information (e.g., faces).

6. PROCEDURES

Describe all procedures involving human subjects for this protocol. Include copies of all surveys and research measures.

Phase 1: People belonging to groups at risk of HIV (including men who have sex with men, transgender women, female sex workers, and people who inject drugs) and people living with HIV will be recruited to engage in a Photovoice study. An online version of the Photovoice study will be offered during the COVID-19 pandemic, while social distancing is recommended. An in-person version will be offered once social distancing is no longer necessary.

Online procedures: Participants will be involved in the study for one week. On the first day, participants will talk with a study research assistant via WhatsApp. The research assistant will introduce the study, obtain informed consent, share the study website with participants, and guide participants through the introductory videos. Over the following week, participants will take photographs in response to prompts. They will submit their photographs, along with a short story to accompany the photograph, via the study website. Prompts include:

- What makes you happy?
- What makes you sad?
- What is important to you?
- What challenges do you face?
- What do you want doctors to know about you?
- How do you think doctors see you?

In-person procedures: Participants will be involved in the study for one week, including two day-long workshops with several days of taking photographs in between the workshops. At the first workshop, they will learn about photography from a professional photographer. Over the next several days, they will take photographs of their surroundings using either their cell phone or a camera provided by the study team. Participants will respond to the prompts listed above. At the second workshop, they will learn more about photography and story-telling and write a story to accompany their photographs. Workshops will only be open to research participants.

The photographs and stories will be turned into Photovoice presentations (i.e., 2-3 minute

narrated photograph montage), narrated by a member of the study team. These presentations will be incorporated into our intervention (see Phases 3 and 4). Consistent with traditions of photovoice studies (which are a form of Participatory Action Research) and as requested by our community partners, participants will have an opportunity for their final PhotoVoice presentation to be shared with an audience of community stakeholders for advocacy purposes (Wang & Redwood-Jones, 2001). Agreeing to share PhotoVoice presentations is not a prerequisite of participation: Participants can participate in the study without agreeing to share their photovoice presentations with a community audience. Our permission form for sharing photographs is included with our measures and was deemed appropriate for the local context by the University of Malaya IRB.

Phase 2: *Clinicians will be recruited to engage in an online focus group lasting for 3 days. Recruitment flyers will be posted, with permission, to social media sites of local professional organizations. The recruitment flyers will direct interested individuals to a Qualtrics survey containing the study consent form and a brief questionnaire including items measuring socio-demographics, focus groups preferences (i.e., weekends versus weekdays), and contact details (i.e., email address). A research assistant will contact interested individuals to sign them up for focus groups. Four separate groups will be conducted (n=10 participants per group). Each focus group will focus on a different group of participants at risk of HIV (i.e., men who have sex with men, female sex workers, transgender women, or people who inject drugs). An asynchronous online focus group format will be used in which 2-3 questions will be posted daily over the course of 3 days to a secure website (i.e., FocusGroupIt) by a trained interviewer, and participants will respond to questions at their convenience (similar to Facebook).*

Phase 3: *We will pre-test our intervention protocol with five clinicians on a condensed schedule over the course of two weeks. Participants will sign into Zoom for 5 sessions (each lasting 90 minutes) to engage in the intervention. They will then be invited to participate in an in-depth interview regarding their perceived acceptability and feasibility of the intervention.*

Phase 4: *We will pilot test our intervention protocol with clinicians and compare it to two other intervention arms. Clinicians will be randomly assigned to one of three training conditions:*

1. *Participants randomized to the first control condition (n=26) will complete HIV Connect, which is an online course developed by the Malaysian Society of HIV Medicine designed to educate primary care physicians in Malaysia about HIV. It consists of a series of 9 modules and accompanying assessments featuring HIV infectious disease experts who instruct on topics including epidemiology and natural history of HIV, pre-exposure prophylaxis (PrEP) and post-exposure prophylaxis (PEP), sexual history taking and STI testing, and others. Participants will complete 1 module and assessment per month so that the intervention is delivered along the same timeline as the other two conditions (i.e., 9 months). The course is available free of charge to all registered medical practitioners in Malaysia. Clinicians earn Continuing Medical Education credits after completing each module and assessment, and a certificate of completion upon finishing all modules and assessments.*
2. *Participants randomized to the second control condition (n=26) will complete the standard version of Project ECHO for HIV Prevention, without added evidence-based stigma reduction tools. Participants will meet with the Project ECHO® Hub specialists and their learning community on a bi-weekly basis for 90 minutes over the course of 9 months. Their Hub specialists will include the infectious disease, mental/behavioral health, and family medicine specialists, but exclude the stigma expert and community representative. They will be joined periodically by guest*

speakers with expertise in infectious disease, pharmacology, case management, and other clinical topic areas. Each session will feature a didactic training incorporating standardized procedures for HIV testing, prevention, and/or linkage to care, and patient case presentation and discussion.

3. *Participants randomized to our intervention (n=26) will complete Project ECHO® for HIV Prevention intervention with added evidence-based stigma reduction tools. Participants will meet with the Project ECHO® Hub specialists and their learning community on a bi-weekly basis for 90 minutes over the course of 9 months. Their Hub specialists will include the infectious disease, mental/behavioral health, and family medicine specialists, as well as the stigma expert and community representative. The stigma expert and community representative will monitor discussion and address stigmatizing content (e.g., via discussion and didactic training), thereby shaping social norms. The Hub specialists will be joined periodically by guest speakers with expertise in infectious disease, pharmacology, case management, and other clinical topic areas as well as stigma and key population communities. Each session will feature a didactic training, key population Photovoice presentation, and patient case presentation. In addition to addressing HIV testing, prevention, and linkage to care through the presentation of standardized procedures to facilitate education and behavioral design, didactic trainings will include content to increase education surrounding key populations. Weekly Photovoice presentations will facilitate extended contact with key populations and PLWH. Patient-case presentation and discussion will highlight at least one patient from a key population per week, facilitating clinical skills for and changing social norms surrounding working with key populations.*

All phase 4 participants will be invited to complete surveys. A subset of participants (up to 10 per condition) will be invited to participate in focus groups at the end of the intervention.

Citation: Wang, C. C. & Redwood-Jones, Y. A. (2001). Photovoice ethics: Perspectives from Flint photovoice. *Health Education & Behavior*, 28(5), 560-572.

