Phases 2-3: We plan to recruit clinicians by emailing information about the study to members of the Malaysian Medical Association and via established informal networks on social media such as DOBBS (Doctors Only Bulletin Board System) and the Malaysian Primary Care Network. To date, we have had success recruiting Malaysian clinicians via email (participation ranging from 33.4-39.6% of clinicians contacted via email).

Phase 4: We will recruit clinicians from the memberships of the Malaysian Medical Association, Family Medicine Association of Malaysia (FMSA), and Malaysian Primary Care Network. The organizations will share an advertisement to their social media site, which will direct participants to Qualtrics. Participants will be given more information about the study and consent to completing a brief survey and being assigned to a study condition (i.e., step 1 consent). They will then be randomly assigned to a study condition. Clinicians' previous experience with HIV testing will be taken into account in the randomization process to ensure equal distribution of previous experience among study conditions. Once they have been assigned, we will contact them again, provide additional information about their condition, and consent them to the full study (i.e., step 2 consent).

Describe what exclusionary criteria, if any will be applied.

Clinicians who participate in the Phase 3 pre-test will not be eligible to participate in the Phase 4 pilot test.

Describe what (if any) conditions will result in PI termination of subject participation.

N/A

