Phase 4: *Quantitative analyses will be conducted in R version 3.6.2 and include an examination of descriptive statistics and generalized linear models. We will examine changes in mean self-reported stigma (i.e., prejudice, stereotypes, and discrimination) across the 3 time-points of data collection. We will use a two-way repeated measures ANOVA to determine whether any change in stigma is associated with the interaction between the type of condition (factor one) and time (factor two). Qualitative analyses will follow the same*

analytic steps and use the same software as those that we will apply Phases 1-3, except that our analysis will focus on interview transcripts. All qualitative focus groups will be transcribed by our trained research assistants. Results are expected to provide insight into the acceptability and feasibility of the intervention, including barriers to and facilitators of implementation and reasons for withdrawal, as well as participants' perceptions of impact on stigma and care delivery.

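### Both ECHO arms are taught in learning communities, but the specified ANOVA treats the 78 clinicians as independent; if communities differ in change, p-values are too small for conclusions beyond the groups run (minor)

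*Combined protocol and SAP*

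**What the plan says.** The combined protocol and SAP, Section 7 (Phase 4 recruitment), has clinicians consent to a first step; "They will then be randomly assigned to a study condition", with account taken of earlier HIV testing experience. Section 6 gives three arms of 26:

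- Condition 1, HIV Connect, is a self-study online course: "Participants will complete 1 module and assessment per month". No group is described.
- Condition 2, standard ECHO, has clinicians meet every two weeks for 9 months with Hub specialists and a learning community. Sessions include training on HIV testing, prevention and/or "linkage to care, and patient case presentation and discussion".
- Condition 3, ECHO with stigma-reduction tools, has the same format: "Hub specialists and their learning community on a bi-weekly basis for 90 minutes over the course of 9 months". A stigma expert and a community representative are added to "monitor discussion and address stigmatizing content (e.g., via discussion and didactic training), thereby shaping social norms".

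Section 10 (Phase 4) examines mean self-reported stigma "across the 3 time-points of data collection". A two-way repeated measures ANOVA is to determine "whether any change in stigma is associated with the interaction between the type of condition (factor one) and time (factor two"). Quantitative analyses will also "include an examination of descriptive statistics and generalized linear models", but these models are not specified. The document gives no community term, number of communities per arm, ICC, survey timing, alpha or power calculation.

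**The concern.** A repeated measures ANOVA allows for correlation between one clinician's scores over time. It does not allow for correlation between clinicians who share a community. Two of the three arms are delivered in groups that meet for 9 months, and in condition 3 the group discussion is itself meant to change norms about the outcome being measured. It is therefore plausible that clinicians in one community change together.

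If so, an unusually engaged or disengaged community could be reported as a condition-by-time effect. The difference between condition 3 and condition 2 matters most for interpretation, because it isolates the stigma tools, although the plan does not name it as a contrast. Both of its sides may be clustered. Section 8 expects knowledge on the preliminary impact of a strategy intended for wide use, so the result is likely to be read beyond these particular groups.

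**Working it through.** **Plan's own figure.** 3 × 26 = 78, which agrees with Section 5. There is no power calculation to reproduce.

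**Inputs from the documents.** 26 clinicians per arm, 3 arms, 3 time-points, individual randomisation, group delivery in conditions 2 and 3 only. The interaction F test then has (3−1)(3−1) = 4 and (78−3)(3−1) = 150 degrees of freedom.

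**Assumed inputs.** Two-sided alpha of 5%, ICC of the baseline-to-last change of 0.01, 0.05 or 0.10, the number of communities per arm, and no loss to follow-up. None of these is in the documents.

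**Standard error, one community per arm.** Take the total variance of change as 1, let m be the number of clinicians per community (here 26), and let DE = 1 + (m−1) × ICC = 1.25, 2.25, 3.50.

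- The true variance of an ECHO arm's mean change is ICC + (1−ICC)/26 = DE/26. The ordinary analysis estimates (1−ICC)/26.
- Condition 3 minus condition 2, independent communities: the SE is too small by sqrt(DE/(1−ICC)) = sqrt(1.25/0.99), sqrt(2.25/0.95), sqrt(3.50/0.90) = 1.12, 1.54, 1.97.
- The same contrast if half the community variance comes from a hub shared by both arms: that half cancels, leaving sqrt(1 + 13 × ICC/(1−ICC)) = 1.06, 1.30, 1.56.
- ECHO minus HIV Connect, equal total variance in all arms: sqrt((1+DE)/(2−ICC)) = sqrt(2.25/1.99), sqrt(3.25/1.95), sqrt(4.50/1.90) = 1.06, 1.29, 1.54.
- A reported p of 0.05 for condition 3 minus condition 2 (t = 2.009 on 50 df) corresponds to 2 × P(t > 2.009/factor) = 0.08, 0.20, 0.31 with independent communities, or about 0.065, 0.13, 0.20 with half shared.

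**Interaction test, by simulation.** Each cell has 40,000 replicates with no true condition effect. Residual variance is 1 per measurement, so the residual variance of a change is 2. A community shift with variance 2 × ICC/(1−ICC) then gives the stated ICC of change. Except where noted, the shift is the same at both post-baseline surveys.

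| Scenario | ICC 0.01 | ICC 0.05 | ICC 0.10 |
|---|---|---|---|
| Both ECHO arms, one independent community each | 7% | 20% | 35% |
| As above, half the shift at the middle survey | 7% | 16% | 28% |
| As the first row, half the variance from a shared hub | 7% | 16% | 29% |
| Only condition 3 clustered, one community | 6% | 12% | 20% |
| Both ECHO arms, two communities each (13+13) | 6% | 12% | 20% |
| Both ECHO arms, three communities each (9+9+8) | 6% | 9% | 14% |

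At ICC 0, or when a community's shift is constant from baseline onward, the error is about 5%. If independent community effects act on both time contrasts instead of one common shift, the first row becomes about 9, 28 and 49%. The direction is therefore stable, but the size depends on the model.

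**Check of the remedy.** With one independent community per arm, the ordinary 95% interval for condition 3 minus condition 2 covers 91.8, 80.6 and 68.5%. Multiplying the SE by sqrt(DE/(1−ICC)) restores 94.8 to 94.9%.

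**The case against.** The strongest reply is that individual randomisation protects the test. A reader might infer from this point that the ANOVA is simply invalid. The documents do not support that: the test remains valid for the strict null of no effect on anyone, and a conclusion limited to these groups as run is not distorted.

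Four further objections reduce the size:

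- The ICC, the number of communities and the shape of the shift are all assumed, so no single error rate can be claimed. This stands.
- Both ECHO arms list the same three Hub specialist roles. If the same people serve both arms, their influence is common and cancels in condition 3 minus condition 2. The documents do not say whether the individuals are the same, so the factors for independent communities should not be read alone.
- Norm-shaping is described for condition 3 only. Condition 2 has case discussion, so equal clustering in both arms is the less supported scenario. Moreover, an average norm shift in condition 3 is the intended effect. It makes random differences between communities plausible but does not demonstrate them.
- This is a pilot, and the large-scale language in Section 8 describes the purpose of the strategy. It does not claim that this p-value generalises.

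These objections lower the weight but do not remove the point. An inferential interaction test is planned, and nothing in the plan records community membership or limits what the p-value can be used for.

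**Conclusion.** The point holds as a conditional one of minor weight. If communities differ randomly in change after baseline, the specified ANOVA gives standard errors and p-values that are too small for conclusions about the programmes beyond the groups run. The direction is the same for every positive ICC tried. Over an assumed ICC of 0.01 to 0.10, with one community per arm, a common post-baseline shift and no loss to follow-up, the error of the nominal 5% test runs from about 6 to 20% (only condition 3 clustered) to about 7 to 35% (both ECHO arms clustered independently).

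If each ECHO arm is a single community, community and arm effects cannot be separated by any analysis. A reader might take the upper figures as the trial's actual error rate; the documents do not support this, since they give neither an ICC nor a number of communities. With no alpha, power or decision rule stated, the practical consequence is how the interaction p-value is worded and used.

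**What to change.** - Record each clinician's learning community and report the number and size of communities per ECHO arm.
- Report arm differences in change, including condition 3 minus condition 2, with sensitivity 95% intervals over a stated ICC range, for example 0.01 to 0.10. Multiply the ordinary SE by sqrt(DE/(1−ICC)) for ECHO against ECHO, and by sqrt((1+DE)/(2−ICC)) for ECHO against HIV Connect (equal total change variance assumed). DE = 1 + (m−1) × ICC, with m the clinicians analysed per community. With more than one community per arm, replace ICC in the two denominators by ICC × (m−1)/(n−1), where n is the clinicians per arm.
- State that the ECHO-against-ECHO multiplier assumes no shared hub effect and is smaller if the hub is shared.
- Label the interaction p-value exploratory, since the multipliers do not repair the F test. With one community per arm, state that community and arm effects cannot be separated.
- Say how the generalized linear models will handle community membership.

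A partially nested mixed model, with a community-by-time random effect in the ECHO arms only, is optional. It is useful only if there are enough communities to estimate their variance. For condition 3 against condition 2, k communities per arm give about 2(k−1) degrees of freedom: 2 with two communities per arm (critical t 4.30, against 2.01 now) and 4 with three (2.78).

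The cost is one recorded variable and some analysis and reporting text, with no extra participants or sessions. The downside is wider intervals and a more limited conclusion.

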7. STUDY POPULATION AND RECRUITMENT

Describe who and how many subjects will be invited to participate. Include age, gender and other pertinent information.

Phase 1: *Individuals will be eligible to participate if they are: 18 or older and identify as a man who has sex with men, person who injects drugs, transgender woman, female sex worker, or person living with HIV (n=35). Participants completing the in-person version of the study will have to be able to attend two Photovoice trainings held in Kuala Lumpur. Participants completing the online version of the study will have to have access to a cell phone with a camera and internet access.*

Phases 2-4: *Individuals will be eligible to participate if they are: 18 or older, a practicing general practitioner or family medicine specialist, and have internet access (n=123).*

Attach all recruitment fliers, letters, or other recruitment materials to be used. If verbal recruitment will be used, please attach a script.

Recruitment materials have yet to be developed. We will submit an amendment with

recruitment materials when we have developed them.

Phase 1: We will recruit participants at risk of or living with HIV by posting an advertisement for the study on listservs and social media platforms maintained by the Malaysian AIDS Council, Kuala Lumpur AIDS Support Services Society, and PT Foundation, which are organizations that our collaborators at the University of Malaya have long-standing relationships with and serve people at risk of or living with HIV in Kuala Lumpur. Thus, all participants will be affiliated with local HIV-related organizations that serve people at risk of and living with HIV. Participants freely subscribe to these listservs. Interested individuals will email the study coordinator to express interest. The research assistant will then coordinate a phone call via WhatsApp to describe the study and determine eligibility (i.e., verbal confirmation that individual is a member of a risk group for HIV or living with HIV, but not which risk group they belong to). Participants completing the online study will then be introduced to the study website by the research assistant. Participants completing the in-person study will be given information about the location and time for the photography workshop.

Phases 2-3: We plan to recruit clinicians by emailing information about the study to members of the Malaysian Medical Association and via established informal networks on social media such as DOBBS (Doctors Only Bulletin Board System) and the Malaysian Primary Care Network. To date, we have had success recruiting Malaysian clinicians via email (participation ranging from 33.4-39.6% of clinicians contacted via email).

Phase 4: We will recruit clinicians from the memberships of the Malaysian Medical Association, Family Medicine Association of Malaysia (FMSA), and Malaysian Primary Care Network. The organizations will share an advertisement to their social media site, which will direct participants to Qualtrics. Participants will be given more information about the study and consent to completing a brief survey and being assigned to a study condition (i.e., step 1 consent). They will then be randomly assigned to a study condition. Clinicians' previous experience with HIV testing will be taken into account in the randomization process to ensure equal distribution of previous experience among study conditions. Once they have been assigned, we will contact them again, provide additional information about their condition, and consent them to the full study (i.e., step 2 consent).

Describe what exclusionary criteria, if any will be applied.

Clinicians who participate in the Phase 3 pre-test will not be eligible to participate in the Phase 4 pilot test.

Describe what (if any) conditions will result in PI termination of subject participation.

N/A

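### Phase 4 does not screen for availability for the live ECHO sessions before randomisation, which leaves the ECHO arms open to loss or under-treatment of unknown size

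*Combined protocol and SAP*

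**What the plan says.** Section 7 (Study population and recruitment) has one eligibility line for Phases 2-4: "18 or older, a practicing general practitioner or family medicine specialist, and have internet access (n=123". The only further exclusion is that "Clinicians who participate in the Phase 3 pre-test will not be eligible to participate in the Phase 4 pilot test". Neither mentions time or attendance.

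Section 6 (Procedures) gives the three Phase 4 conditions, with 26 clinicians each. Standard ECHO and ECHO with stigma-reduction tools both meet with Hub specialists and a learning community "on a bi-weekly basis for 90 minutes over the course of 9 months". For HIV Connect, "Participants will complete 1 module and assessment per month".

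Under section 7, clinicians consent at step 1 to a brief survey and to being assigned. They are then randomised, taking prior HIV-testing experience into account. Only afterwards do they receive further information about their own condition and consent to the full study (step 2).

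Section 6 invites all Phase 4 participants to the surveys, with no attendance condition. Section 10 (Data) plans a two-way repeated measures ANOVA over three time-points, with the condition-by-time interaction as the test of interest. It names no analysis set, missing-data method or expected dropout.

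Elsewhere the plan does consider availability. For Phase 1, "Participants completing the in-person version of the study will have to be able to attend two Photovoice trainings held in Kuala Lumpur", and the Phase 2 sign-up questionnaire asks about weekday or weekend preference.

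**The concern.** Two arms need a clinician to be present with a group at a set time; the third does not. A practising clinician can meet every criterion, be randomised, and be unable to make the ECHO meeting time. The same clinician assigned to HIV Connect could complete it. A scheduling conflict therefore matters in two arms and hardly at all in the third, and the order of consent lets it surface after allocation.

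Two things are at stake. If these clinicians refuse at step 2 or drop out, the groups analysed for ECHO versus HIV Connect may no longer be the groups randomised. If they remain but attend little, the estimated effect of the ECHO programmes shrinks. With 26 per arm there is little room for either.

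**Working it through.** **Plan's own figures.** Phases 2-4: 40 + 5 + 78 = 123. Phase 4: 3 × 26 = 78. Both reproduce. The documents state no alpha, power, effect size or dropout rate, so there is no power calculation to reproduce. Every rate below is an assumption.

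**Commitment by arm.** Nine months is about 39 weeks. If bi-weekly means every two weeks, each ECHO arm has 39 / 2 = 19.5 sessions, and 19.5 × 1.5 h = 29.25 h of live meetings. If it means twice a week, the total is 78 sessions and 117 h. HIV Connect has nine modules, one a month.

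**Route 1: clinicians leave the analysis (ECHO versus HIV Connect).** Let L be the proportion lost in an arm and D the gap in outcome, in SD, between lost and retained clinicians, taken as equal in both arms. The retained mean differs from the full-arm mean by L × D, so the contrast shifts by (L in ECHO − L in HIV Connect) × D.

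| Loss in HIV Connect | Loss in ECHO | D = 0 | D = 0.25 | D = 0.5 | D = 0.8 |
|---|---|---|---|---|---|
| 10% | 10% | 0 | 0 | 0 | 0 |
| 10% | 20% | 0 | 0.025 | 0.05 | 0.08 |
| 10% | 30% | 0 | 0.05 | 0.10 | 0.16 |
| 10% | 50% | 0 | 0.10 | 0.20 | 0.32 |
| 0% | 50% | 0 | 0.125 | 0.25 | 0.40 |

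For the planned test, D must be a gap in *change*. If lost clinicians sit a constant amount higher or lower at every time-point but change by the same amount, that constant cancels within each clinician. A 20% loss with a 0.5 SD gap in level moves the retained mean by 0.2 × 0.5 = 0.1 SD at each time-point, and the retained change by zero.

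For scale, a simple two-arm contrast at two-sided 5% and 80% power (normal approximation) detects (1.96 + 0.84) × √(1/26 + 1/26) = 0.78 SD. With 30% versus 10% loss (about 18 versus 23) it detects 0.88 SD.

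**Route 2: precision and dilution (ECHO-plus versus ECHO).** The schedules match, so equal proportions p are assumed unable to attend in both arms. The reference difference is 0.79 SD, which is simply the value giving 80% power at 26 per arm (two-sample t-test, two-sided 5%). If those clinicians are lost, n falls to 26 × (1 − p). If they stay and gain nothing, n remains 26 and the difference becomes 0.79 × (1 − p).

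| p | n per arm if lost | Power if lost | Difference if they stay | Power if they stay |
|---|---|---|---|---|
| 0% | 26 | 80% | 0.79 | 80% |
| 10% | 23 | 75% | 0.71 | 71% |
| 20% | 21 | 71% | 0.63 | 61% |
| 30% | 18 | 64% | 0.55 | 50% |

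**The case against.** A reader might infer that clinicians who cannot attend *will* be lost, mainly from the ECHO arms, and that the comparison with HIV Connect is therefore biased. The documents do not support that.

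- They give no attrition figure, overall or by arm.
- They do not call the session times fixed. Slots could be chosen around participants or offered more than once, although no alternative or make-up sessions are described.
- Missing sessions is not missing outcome data. All Phase 4 participants are invited to the surveys, and section 9 (Compensation) pays them for completing surveys. A non-attender who responds dilutes the effect and does not alter who is compared.
- A gap in stigma level between lost and retained clinicians does not bias a test of change. The 0.1 SD shift in level is not evidence of bias in the planned analysis.
- The step 1 information, brief survey, consents and recruitment flyers are not available to read. The schedule may be disclosed there, so it cannot be said that clinicians are not told of it before assignment.
- The power losses are what any equal loss or dilution would produce; they do not measure how often unavailability occurs.
- The comparators are imperfect: Phase 1 concerns physical attendance, and Phase 2 records a preference, not a criterion.
- This is a pilot that aims to learn about feasibility and reasons for withdrawal, so randomising ordinary clinicians is defensible.

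All of this limits what can be claimed about size and direction. The gap itself stands. Disclosure at step 1, if it happens, is not a stated eligibility requirement, and any single group meeting time will exclude someone. Nor can an analysis rule for step 2 refusals restore exposure for clinicians who could never attend.

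**Conclusion.** The point holds as a design gap with a conditional consequence. Availability for the live sessions is not an eligibility criterion, the arms differ sharply in scheduled commitment, and full consent follows allocation. Loss or under-treatment tied to scheduling can therefore arise in the ECHO arms without a counterpart in HIV Connect.

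Its size is unknown. Under the assumed rates, the shift in ECHO versus HIV Connect runs from zero to 0.40 SD. It is zero whenever losses are equal across arms or those lost change as the others do. ECHO-plus versus ECHO gains no obvious bias, but its power for a 0.79 SD difference would fall from 80% to between 75% and 50% if 10% to 30% could not attend, depending on whether they leave or stay untreated. These ranges rest on assumed losses, an assumed gap in change and, for dilution, no benefit to non-attenders. They show what is possible and do not predict what will happen.

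**What to change.** Set the ECHO session slot or slots before recruitment and state them in the step 1 information. Add an eligibility item, answered by every clinician before randomisation whatever the eventual arm: able to attend the bi-weekly session time for 9 months if assigned. Because it applies to all three arms before allocation, the randomised groups stay comparable. Report the number screened out for unavailability as a feasibility result.

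The cost is one screening question and one eligibility line. The eligible pool becomes somewhat smaller, and the results will apply to clinicians who can attend scheduled sessions. Some information on scheduling barriers leaves the randomised sample; the screened-out count recovers much of it.
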